9.4.2. Vital Signs

- Heart rate (HR), respiratory rate, systolic and diastolic blood pressure (BP), and temperature will be assessed; the method for measuring temperature will be per the site's preference.
- BP and HR measurements will be assessed in the sitting position with a completely automated device. Manual techniques will be used only if an automated device is not available.
- BP and HR measurements should be preceded by at least 3 minutes of rest for the participant in a quiet setting without distractions (eg, television, cell phones).
- Vital signs are to be taken before blood collection for laboratory tests.

Relamorelin

9.4.3. Electrocardiograms

- Single 12-lead ECG will be obtained as outlined in the SoA (Section 2) using an ECG machine that automatically calculates the heart rate and measures PR, QRS, QT, and QTc intervals. Refer to Section 8.1 for QTc withdrawal criteria; also see Section 9.2.7.3, Major Adverse Cardiovascular Events.

9.4.4. Clinical Safety Laboratory Assessments

- See Appendix 2 for the list of clinical laboratory tests to be performed and refer to the SoA (Section 2) for the timing and frequency.
- The investigator must review the laboratory report, document this review, and record any clinically relevant changes occurring during the study in the AE section of the eCRF. The laboratory reports must be filed with the source documents. Clinically significant abnormal laboratory findings are those that are not associated with the underlying disease, unless judged by the investigator to be more severe than expected for the participant's condition.
- All laboratory tests with values considered clinically significantly abnormal during participation in the study or within 30 days after the last dose of study treatment should be repeated until the values return to normal or baseline, or are no longer considered clinically significant by the investigator or MSP.
 - If such values do not return to normal/baseline within a period of time judged reasonable by the investigator, the etiology should be identified and the sponsor notified.
 - All protocol-required laboratory assessments, as defined in Appendix 2, must be conducted in accordance with the laboratory manual and the SoA (Section 2).
 - If laboratory values from non-protocol specified laboratory assessments performed at the institution's local laboratory require a change in participant management or are considered clinically significant by the investigator (eg, SAE or AE or dose modification), then the results must be recorded in the eCRF.

Relamorelin

9.4.5. Self-monitoring of Blood Glucose

Participants will be strongly encouraged to carry out self-monitoring of blood glucose (SMBG) at home in order to achieve and maintain optimum glucose control during the study. This is almost always required by patients with T1DM and is good clinical practice in patients with T2DM. Sponsor will provide each participant with test strips and all supplies necessary for testing finger-stick capillary blood glucose with the glucose monitor previously provided in lead-in study RLM-MD-01 or RLM-MD-02. It is recommended that this be done twice daily, pre-breakfast (fasting) and approximately 2 hours post-lunch or dinner (whichever is the larger meal).

Information from SMBG, in addition to that provided by values of HbA1c and fasting blood glucose, will be available to investigators for decision-making regarding adjustment of diabetic medications, diet, and exercise (or, alternatively, for decision-making regarding referral of the patient to his/her health care provider for the same purpose).

9.5. Pharmacokinetics

Pharmacokinetic parameters are not evaluated in this study.

9.6. Pharmacodynamics

Pharmacodynamic parameters are not evaluated in this study.

[figure not shown]
9.7. Genetics

Genetics are not evaluated in this study.

9.8. Biomarkers

Biomarkers are not used in the study.

Relamorelin

10. Statistical Considerations

10.1. Sample Size Determination

Enrollment in this study is dependent upon the drop-out rates in the pivotal studies RLM-MD-01 and RLM-MD-02. Assuming 300 participants per arm in each study and a drop-out rate of 20% in each of the pivotal studies, it is expected that approximately 960 participants (480 participants in each arm) will enter the study. Further, assuming that the drop-out rate will also be 20% by Week 12 in this study, it is expected that there will be 384 participants per treatment group at Week 12. This sample size will provide 99% power to detect a statistically significant difference in response rate between treatment and placebo in both the 4-symptom composite DGSSS endpoint (assuming a placebo rate of 14% and a treatment rate of 35%) and in the vomiting response endpoint (assuming a placebo rate of 11% and a treatment rate of 26%.) at Week 12. The assumed response rates were those calculated from study RM-131-009.

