
Primary
 
 • To compare the efficacy of relamorelin with that of placebo after 12 weeks of treatment in this study (ie, after a total of 24 weeks of treatment—12 weeks from lead-in study RLM-MD-01 or from lead-in study RLM-MD-02 and 12 weeks from the current study) in participants with DG with respect to the following core signs and symptoms of DG: 
 • Nausea • Abdominal pain • Postprandial fullness • Bloating • To compare the efficacy of relamorelin with that of placebo after 12 weeks of treatment in this study (ie, after a total of 24 weeks of treatment—12 weeks from lead-in study RLM-MD-01 or from lead-in study RLM-MD-02 and 12 weeks from the current study) in participants with DG with respect to vomiting frequency 	
Primary
 
 • Change from Baseline to Week 12 of this study in the weekly Diabetic Gastroparesis Symptom Severity Score (DGSSS) • Vomiting Week-12 Responder, defined as a participant with zero weekly vomiting episodes during each of the last 6 weeks of the first 12-week Treatment Period.

Secondary
 
 • To compare the efficacy of relamorelin with placebo after 12 weeks of treatment in this study (ie, after a total of 24 weeks of treatment—12 weeks from lead-in study RLM-MD-01 or from lead-in study RLM-MD-02 and 12 weeks from the current study) in participants with DG with respect to the following individual symptoms of the DGSSS: 
 • Nausea • Abdominal pain • Postprandial fullness • Bloating 	
Secondary
 
 • Individual Symptom (ie, nausea, abdominal pain, postprandial fullness, and bloating) Week-12 Responder

Relamorelin

Objectives	Endpoints

 To compare the efficacy of relamorelin with placebo after 40 weeks of treatment in this study (ie, after a total of 52 weeks of treatment—12 weeks from the lead-in study RLM-MD-01 or lead-in study RLM-MD-02 and 40 weeks from the current study) in participants with DG with respect to the following core signs and symptoms of DG: 
 Nausea Abdominal pain Postprandial fullness Bloating 	
 Change from Baseline (CFB) to Week 40 in the average weekly DGSSS

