4.2. Clinical Hypotheses

The clinical hypotheses are:

- DG participants receiving relamorelin compared with DG participants receiving placebo will experience greater improvement in DGSSS.
- A greater proportion of DG participants receiving relamorelin than DG participants receiving placebo will achieve “Vomiting Week-12 Responder” status, defined as a participant with zero weekly vomiting episodes during each of the last 6 weeks of the 12-week Treatment Period.

Relamorelin

3. A greater proportion of DG participants receiving relamorelin than DG participants receiving placebo will achieve “Week-12 Responder” status for the individual symptoms comprising the DGSSS (nausea, abdominal pain, bloating, post-prandial fullness), defined as experiencing a clinically meaningful ≥ 2 -point improvement in the symptom severity score during each of the last 6 weeks of the first 12 weeks of the Treatment Period.
4. Improvements in DGSSS and number of vomiting episodes will be seen through Week 40 (ie, Week 52 [the combination of treatment duration of the current study and the 12-week treatment duration from either lead-in study RLM-MD-01 or lead-in study RLM-MD-02]).
5. Participants who are treated with relamorelin during the Treatment Period, and randomized to relamorelin during the RWP will experience maintenance of effect of treatment compared to participants who are randomized to placebo in the RWP.

5. Study Design

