CFB ANCOVA	
 • Continuous descriptives and standard error (SE) for baseline, postbaseline, and CFB values • Estimates derived from mixed model for CFB value controlling for factors (treatment group, region) and covariates (baseline value) 
 ○ Least squares (LS) means and standard errors ○ LS mean differences, standard errors, and confidence intervals vs placebo ○ P-values from contrast t-test comparing treatment group vs placebo • N1 = participants with nonmissing values at both baseline and the specified postbaseline analysis visit
CFB MMRM	
 • Continuous descriptives and standard error (SE) for baseline, postbaseline, and CFB values • MMRM model with geographic region, treatment, week, treatment-by-week interaction as factors, baseline and baseline-by-week interaction values as covariates • Estimates derived from mixed model for CFB value controlling for factors (treatment group, region) and covariates (baseline value) 
 ○ Least squares (LS) means and standard errors ○ LS mean differences, standard errors, and confidence intervals vs placebo ○ P-values from contrast t-test comparing treatment group vs placebo • N1 = participants with nonmissing

Relamorelin

Methodology	Description
Responder	
 • Categorical descriptives for responders and non-responders 
 ○ Nonresponders include: 
 ▪ Participants who do not meet responder criteria ▪ Participants with no postbaseline values • Risk differences and Wald confidence intervals vs [placebo/active comparator] • Estimates derived from Cochran-Mantel-Haenszel (CMH) model controlling for factors (treatment group, region) 
 ○ Mantel-Haenszel (MH) odds ratios (ORs) and confidence intervals vs placebo ○ P-values comparing treatment group vs placebo • N1 = all participants unless otherwise specified

ANCOVA = analysis of covariance; CFB = change from baseline; MMRM = mixed-effects model with repeated measures.

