10.3.2. Efficacy Analyses

10.3.2.1. Key Endpoints

Table 10-3 displays the primary and secondary efficacy endpoints that will be analyzed for the mITT population. For all analyses, the baseline is the baseline value from the lead-in study RLM-MD-01 or RLM-MD-02. All other efficacy endpoints and analyses will be defined in the SAP.

Table 10-3 Key Endpoints

Key Endpoints	Description	Timing	Methodology
Primary			
CFB to Week 12 in weekly DGSSS	Change from baseline to week 12 of this study in the weekly DGSSS. Weekly score at Week 12: Average score from Days 78 to 84.	Days 78 to 84	CFB MMRM
Vomiting Week 12 Responder	Vomiting responder defined as a participant with zero weekly vomiting episodes during each of the last 6 weeks of the first 12 weeks of the Treatment Period.	Last 6 weeks of the first 12 weeks of the 40-week Treatment Period	Responder
Secondary			
Nausea Week 12 Responder	Nausea responder defined as a participant who has a ≥ 2 -point improvement in the weekly symptom score at each of the last 6 weeks of the first 12 weeks of the 40-week Treatment Period	Last 6 weeks of the first 12 weeks of the 40-week Treatment Period	Responder
Abdominal Pain Week 12 Responder	Abdominal pain responder defined as a participant who has a ≥ 2 -point improvement in the weekly symptom score at each of the last 6 weeks of the first 12 weeks of the 40-week Treatment Period	Last 6 weeks of the first 12 weeks of the 40-week Treatment Period	Responder

Relamorelin

Table 10-3 Key Endpoints

Key Endpoints	Description	Timing	Methodology
Bloating Week 12 Responder	Bloating responder defined as a participant who has a ≥ 2 -point improvement in the weekly symptom score at each of the last 6 weeks of the first 12 weeks of the 40-week Treatment Period	Last 6 weeks of the first 12 weeks of the 40-week Treatment Period	Responder
Postprandial Fullness Week 12 Responder	Postprandial Fullness responder defined as a participant who has a ≥ 2 -point improvement in the weekly symptom score at each of the last 6 weeks of the first 12 weeks of the 40-week Treatment Period	Last 6 weeks of the first 12 weeks of the 40-week Treatment Period	Responder
DGSSS at Week 40	Change from baseline to Week 40 in average weekly DGSSS. Average weekly scores are derived as the average of the weekly scores from the four weeks prior to Week 40 (Visit 7) in this study.	Week 36 - Week 40	CFB ANCOVA

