10.3.2.2. Missing Data

Participants with a missing weekly value for either of the key endpoints (symptom Week 12 responders or vomiting frequency) during any of the last 6 weeks of the first 12 weeks of the 40-week Treatment Period will be analyzed as a non-responder for the particular endpoint for the Week-12 responder analyses.

Participants with a missing weekly value for either of the key endpoints (symptom Week 40 responders or vomiting frequency) during any of last 4 weeks of the 40-week Treatment Period will be analyzed as a non-responder for the particular endpoint for the Week-40 responder analyses.

Relamorelin

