10.1 Primary Efficacy Endpoints

- **Change from Baseline to Week 12 in Weekly DGSSS:** Baseline is the baseline value from the lead-in study RLM-MD-01 or RLM-MD-02 and Week 12 is the 12th week of the 40-week Treatment Period (Days 78 to 84).
- **Vomiting Week-12 Responder:** Vomiting Week-12 Responder is defined as a participant with zero weekly vomiting episodes during each of the last 6 weeks of the first 12 weeks of the 40-week Treatment Period.

A participant will be considered as Vomiting Week 12 non-Responder if the weekly number of vomiting episodes is missing from the diary for any of the last 6 weeks of the first 12 weeks of the 40-week Treatment Period.

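### Protocol 10.1 states 99% power for a composite DGSSS response rate, but the DGSSS primary endpoint is a change from baseline, so that primary has no stated power

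*Protocol*

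**What the plan says.** Protocol 10.1 expects 384 participants per arm at Week 12 and states "99% power to detect a statistically significant difference in response rate between treatment and placebo in both the 4-symptom composite DGSSS endpoint" (14% on placebo, 35% on relamorelin) and in the vomiting response endpoint (11% and 26%). The rates are said to come from the Phase 2b study RM-131-009.

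Elsewhere the DGSSS primary is continuous. Table 10-3 describes it as "Change from baseline to week 12 of this study in the weekly DGSSS", taken over Days 78 to 84, and assigns it to the CFB MMRM method. Table 10-2 specifies that method as "MMRM model with geographic region, treatment, week, treatment-by-week interaction as factors", with baseline and baseline-by-week as covariates. Protocol Section 4 and the Synopsis define the endpoint the same way, and SAP 10.1 lists "Change from Baseline to Week 12 in Weekly DGSSS". Clinical hypothesis 1 in Protocol 4.2 reads "DG participants receiving relamorelin compared with DG participants receiving placebo will experience greater improvement in DGSSS", whereas hypotheses 2 and 3 are about proportions.

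The responder endpoints in Protocol Table 10-3 and SAP 10.1 and 10.2 are vomiting (Weeks 12 and 40) and the four single symptoms (Week 12). The DGSSS secondaries, at Week 40 and at the end of the randomized-withdrawal period, are changes from baseline.

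**The concern.** The trial has two primary endpoints, one for DGSSS and one for vomiting. Protocol 10.1 names one DGSSS endpoint and one vomiting endpoint and attaches 99% power to both. A reader may well take this as the power for both primaries. For vomiting the quantity powered matches the primary. For DGSSS it does not: a difference between two proportions has been powered, while the primary test compares mean changes.

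Power for the one does not fix power for the other. A comparison of means needs an assumed mean difference and SD, and neither document gives them. One of the two primaries therefore has no stated power basis.

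**Working it through.** **Inputs.** Two-sided 5% tests without multiplicity adjustment (Protocol 10.3.1). From Protocol 10.1: 300 per arm in each of two lead-in studies, 20% drop-out there and a further 20% by Week 12, and the response rates above.

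**Sample size.** 2 × 300 × 0.8 = 480 per arm entering (960 in total). 480 × 0.8 = 384 per arm at Week 12. Both agree with the protocol.

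**The plan's own figure.** Normal approximation with pooled variance under the null:

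power = Φ[(Δ − 1.960·SE0) / SE1], where SE0 = √(2·p̄(1 − p̄)/n) and SE1 = √([p1(1 − p1) + p2(1 − p2)]/n).

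- DGSSS response, 14% vs 35%, n = 384: SE0 = 0.03104, SE1 = 0.03010. (0.21 − 0.06084)/0.03010 = 4.96, power 0.9999996.
- Vomiting response, 11% vs 26%, n = 384: SE0 = 0.02802, SE1 = 0.02750. (0.15 − 0.05492)/0.02750 = 3.46, power 0.99973.

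The stated 99% is therefore met for both response rates.

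**Does 99% for vomiting survive the missing-data rule?** Under Protocol 10.3.2.2 a participant with a missing weekly value in the relevant six weeks "will be analyzed as a non-responder for the particular endpoint for the Week-12 responder analyses". Suppose 11% and 26% are rates among those still in the study, and the 20% who drop out count as non-responders among 480 per arm. The rates become 0.8 × 11% = 8.8% and 0.8 × 26% = 20.8%, and power is 0.99955. If 11% and 26% already count drop-outs as non-responders, n = 480 gives 0.99998. The vomiting claim stands either way.

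**The DGSSS primary as defined.** For a simple two-group comparison of means, the detectable standardized difference is d = (1.960 + z_power)/√(n/2).

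| Power | n = 384 per arm | n = 480 per arm |
|---|---|---|
| 80% | 2.802/13.856 = 0.202 SD | 2.802/15.492 = 0.181 SD |
| 90% | 3.242/13.856 = 0.234 SD | 3.242/15.492 = 0.209 SD |
| 99% | 4.286/13.856 = 0.309 SD | 4.286/15.492 = 0.277 SD |

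The noncentral t distribution changes these by less than 0.001 SD. No gain from baseline adjustment or repeated measures is included, so these are not the power of the planned MMRM.

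**How far the answer depends on the missing inputs.** The SDs and the difference here are assumptions for illustration, not estimates from the documents. At 384 per arm:

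| Assumed SD (DGSSS points) | Difference needed for 99% power | Power if the true difference is 2 points |
|---|---|---|
| 6 | 1.86 | 99.6% |
| 8 | 2.47 | 93.4% |
| 10 | 3.09 | 79.1% |
| 12 | 3.71 | 63.7% |

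The 99% may or may not hold for the DGSSS change. The documents do not allow it to be settled.

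**The case against.** **A composite responder might exist elsewhere.** Table 10-3 covers the primary and secondary endpoints, and Protocol 10.3.2.1 adds "All other efficacy endpoints and analyses will be defined in the SAP". The SAP abbreviation list keeps a term for a DGSSS study responder, and Protocol 9.1.1 calls a DGSSS fall of at least 10 points clinically meaningful. The SAP available is abbreviated, so a composite responder at another level cannot be excluded. This limits the claim to listed primary and secondary endpoints. It does not help Protocol 10.1, because such an endpoint would still not be the DGSSS primary.

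**The practical stakes are small.** Enrolment followed from rollover out of the lead-in studies, not from this calculation. The study was terminated early, SAP 10 makes efficacy descriptive, and SAP 13 presents the sample-size text as the original design with objectives that no longer apply. All of this stands. Protocol 10.1 carries no such label, however, and remains the stated design rationale.

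**Protocol 10.1 never uses the word primary.** It speaks openly of response rates, so the misreading is possible rather than certain. That is fair, though pairing DGSSS with vomiting makes it likely.

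**The replacement figures are not MMRM power either.** The MMRM, run in the mITT population, can use weekly data from people who leave before Week 12. This also stands, and is why the replacement must be labelled as a simple approximation. Deleting the DGSSS clause would also remove the inconsistency, but would leave the reader with nothing on that endpoint.

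**Amending the protocol of a terminated study is disproportionate.** This bears on where the correction is recorded, not on whether the text is wrong.

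**Conclusion.** The concern holds. The 99% in Protocol 10.1 is arithmetically right for the response rates it names, and it applies to the vomiting primary. It does not apply to the DGSSS primary, for which the documents state no power and give no inputs to derive one. On the simple two-group approximation (two-sided 5%, 384 per arm), 99% power for that endpoint would need a true difference of about 0.31 SD; 80% and 90% need about 0.20 and 0.23 SD.

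This is a mismatch between sections of the current text, not a calculation error, and it is no evidence that the trial was underpowered. The statement should be corrected because it concerns a primary endpoint, but the impact is low.

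**What to change.** In Protocol 10.1, remove the DGSSS response-rate power and keep 99% (11% vs 26%) for the vomiting responder endpoint only. In place of the DGSSS clause, state:

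> With 384 participants per group at Week 12, a simple two-sided 5% two-group comparison (no gain assumed from baseline adjustment or repeated measures) has 80%, 90% and 99% power for a true difference of about 0.20, 0.23 and 0.31 SD in change from baseline to Week 12 in weekly DGSSS.

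Add the assumed mean difference and SD if the sponsor holds them. Without these, the sentence gives detectable differences and should not be read as the power of the MMRM. A clarifying line in SAP 13 is optional, since that section already labels the text as the original design.

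The cost is one replaced sentence, plus whatever approval a protocol amendment needs under Appendix 3. Sample size, conduct and analysis do not change. If no further amendment is planned, the same correction can be recorded in SAP 16 or the study report.

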10.2. Populations for Analyses

The analysis populations will consist of participants as defined in [Table 10-1](#).

Table 10-1 Analysis Populations

Population	Definition
Screened	All participants who sign the ICF
Intent-to-treat (ITT)	All participants who enter the 40-week Treatment Period
Modified intent-to-treat (mITT)	All participants in the ITT Population who have ≥ 1 postbaseline assessment of DGSSD
Safety	All participants in the ITT Population who received ≥ 1 administration of study treatment

10.3. Statistical Analyses

The statistical analysis plan (SAP) will be developed and finalized before database lock and will describe the participant populations to be included in the analyses, and procedures for accounting for missing, unused, and spurious data. This section is a summary of the planned statistical analyses of the primary and secondary endpoints.

10.3.1. Key Statistical Methodology

The methodologies defined in [Table 10-2](#) apply as specified to individual endpoints defined in this SAP. All statistical tests will be 2-sided hypothesis tests performed at the 5% level of significance for main effects without multiplicity adjustment. All confidence intervals will be 2-sided 95% CIs, unless stated otherwise.

Relamorelin

Table 10-2 Statistical Methodology

Methodology	Description
Categorical counts	
 • Number of participants in individual categories 
 ○ Participants with ≥ 1 qualifying event counted once per individual category
Categorical descriptives	
 • Number and percentage of participants in individual categories 
 ○ Participants with ≥ 1 qualifying event counted once per individual category • N1 if percentage denominator \neq number of participants in the population (standard percentage denominator) 
 ○ N1 = participants with nonmissing baseline value
Event descriptives	
 • Number and percentage of events in individual categories 
 ○ Events counted individually for each instance • Percentage denominator = total number of events
Shift analysis	
 • Number and percentage of participants in individual baseline and postbaseline categories • Percentage denominator = number of participants in individual baseline categories • N1 = participants with nonmissing values at both baseline and the specified postbaseline analysis visit
Continuous descriptives	
 • N1, mean, standard deviation, median, minimum, maximum • N1 = participants with nonmissing value
CFB descriptives	
 • Continuous descriptives for baseline, postbaseline, and change from baseline (CFB) values • N1 = participants with nonmissing values at both baseline and the specified postbaseline analysis visit
CFB ANCOVA	
 • Continuous descriptives and standard error (SE) for baseline, postbaseline, and CFB values • Estimates derived from mixed model for CFB value controlling for factors (treatment group, region) and covariates (baseline value) 
 ○ Least squares (LS) means and standard errors ○ LS mean differences, standard errors, and confidence intervals vs placebo ○ P-values from contrast t-test comparing treatment group vs placebo • N1 = participants with nonmissing values at both baseline and the specified postbaseline analysis visit
CFB MMRM	
 • Continuous descriptives and standard error (SE) for baseline, postbaseline, and CFB values • MMRM model with geographic region, treatment, week, treatment-by-week interaction as factors, baseline and baseline-by-week interaction values as covariates • Estimates derived from mixed model for CFB value controlling for factors (treatment group, region) and covariates (baseline value) 
 ○ Least squares (LS) means and standard errors ○ LS mean differences, standard errors, and confidence intervals vs placebo ○ P-values from contrast t-test comparing treatment group vs placebo • N1 = participants with nonmissing

Relamorelin

Methodology	Description
Responder	
 • Categorical descriptives for responders and non-responders 
 ○ Nonresponders include: 
 ▪ Participants who do not meet responder criteria ▪ Participants with no postbaseline values • Risk differences and Wald confidence intervals vs [placebo/active comparator] • Estimates derived from Cochran-Mantel-Haenszel (CMH) model controlling for factors (treatment group, region) 
 ○ Mantel-Haenszel (MH) odds ratios (ORs) and confidence intervals vs placebo ○ P-values comparing treatment group vs placebo • N1 = all participants unless otherwise specified

ANCOVA = analysis of covariance; CFB = change from baseline; MMRM = mixed-effects model with repeated measures.

